#### **6.4.2.1 Replacement policy**

For participants discontinued from the study for reasons other than safety, the decision to replace them by equal number of newly enrolled participants will be taken by the Sponsor.

### **6.5 Treatment blinding**

This is a participant- and investigator-blinded study. Participants and investigator study staff will remain blind to the identity of the treatment assignment from treatment randomization (Day 1) until clinical database lock. Randomization data are kept strictly confidential until the time of unblinding, and will not be accessible by anyone else involved in the study with the following exceptions:

- Bioanalyst (PK/PD): to enable identification of samples from the remibrutinib treatment arms of the study to facilitate bioanalysis
- Specific vendors whose role in trial conduct requires their unblinding (e.g. IRT)
- Global Clinical Supply (GCS)
- Novartis associates who are involved in the analysis before final database lock described in [Section 4.4](#)

Additionally, participants and investigator study staff will remain blind to the sequence of administration of peanut allergen and placebo allergen during the required DBPCFCs, until unblinding of site staff ONLY to the sequence of allergen and placebo dosing at the completion of DBPCFC part 1B (Screening Visit 3). Both site staff and participant may be unblinded to the sequence of administration following completion of DBPCFC part 2B (Day 28).

The following exception(s) pertain to the blinding of sequence of administration of materials for DBPCFC, allowing unblinding of:

- Site pharmacist or trained staff who will be responsible for randomizing, preparing (reconstituting), dosing and administering the peanut allergen and placebo used during the DBPCFCs
- Global Clinical Supply (GCS)
- Specific vendors whose role in trial conduct requires their unblinding (e.g. IRT)

The following measures must be applied by the study site to keep the participant and study site personnel blinded to the identity of the treatment:

- The identity of the treatments will be concealed by the use of study treatment that are all identical in packaging, labeling, schedule of administration, appearance, taste, and odor.
- The identity of the peanut allergen/placebo will be concealed by responsible site staff to maintain blinding of the participant, investigator and other site staff not involved with the preparation and administration of the product.

Apart from the study drug facilitator, study site staff should **NOT** handle the Investigational Medicinal Product (IMP) and no information regarding the IMP should be discussed with the site study staff.

Participants should be discouraged from comparing experiences with other study participants.

Unblinding will occur in the case of participant emergencies and at the conclusion of the study. Health authorities will be granted access to unblinded data if needed. The appropriate personnel from the study site and Novartis will assess whether study treatment should be discontinued for any participant whose treatment code has been broken for any reason. The investigator must maintain an accurate record of the shipment and dispensing of investigational treatment in a drug accountability log.

The randomization codes associated with participants from whom PK samples are taken will be disclosed to a PK analyst who will keep PK results confidential until final database lock.

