### 3 Study design

Figure 3-1 Study Overview

\* Day 2 visit only needed for site participating in the BAT laboratory assessment

This is a Phase 2 multi-center, randomized, participant- and investigator- blinded, placebo controlled study to assess the safety and clinical efficacy of four dosing regimens of oral remibrutinib versus placebo (CCI for one month (4-5 weeks); CCI for one month (4-5 weeks); CCI for one month (4-5 weeks); placebo for 3 weeks followed by remibrutinib CCI for 1-2 weeks; and placebo for one month (4-5 weeks) in adult participants with a medically confirmed diagnosis of IgE-mediated peanut allergy. Approximately 72 participants will be randomized in this study to one of the five arms (randomization ratio of 2:2:2:1:1). Participants initially assigned to the 3-week placebo arm will receive the first dose of blinded remibrutinib treatment at the Day 22 visit. CCI

The study will include the following:

- 1. Screening period (duration of 4 weeks with 3 required visits):** Written informed consent will be obtained before any study-related assessments or procedures are performed. Consented participants will be assessed for study eligibility during the Screening Visit 1 and will need to meet all eligibility criteria for this visit in order to progress to Screening Visits 2 and 3 (DBPCFC parts 1A and 1B), conduct of the double-blind, placebo-controlled food challenge.

To minimize bias in reaction for individual participants, sequence in which allergen or placebo material is provided will be determined by IRT. Participants who receive placebo-allergen challenge material during DBPCFC part 1A will receive peanut-allergen challenge material during DBPCFC part 1B; while those who receive peanut-allergen challenge material during DBPCFC part 1A will receive placebo-allergen challenge material during DBPCFC part 1B. The participant and all study staff, except the unblinded pharmacist/staff member who will re-constitute the allergen, will be blinded to which visit administers which (allergen or placebo).

Those participants who meet threshold requirements for allergen challenge (as described in [Section 5.1](#)) will proceed to the treatment randomization visit and study treatment period.

To ensure participants meet inclusion/exclusion criteria for exposure to both peanut-allergen and placebo-allergen, unblinding of the food challenge will be disclosed a minimum of 30 minutes following the maximum dose of DBPCFC part 1B at screening visit 3.

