### 6.4.2 Treatment assignment, randomization

This study will contain **three** separate time-points of randomization via IRT: randomization of the order in which placebo- or peanut-allergen material is given for the DBPCFC will occur for

the screening DBPCFC (Screening Visits 2 and 3) and again at the one month end-of-treatment DBPCFCs (Days 26 and 28), and randomization to study treatment arm will occur on Day 1.

As the DBPCFC is a double-blinded procedure, it consists of two parts: in one part, the participant is challenged with peanut allergen, and in the other part the participant is challenged with placebo. These challenges take place on different days, and the study staff (other than the unblinded pharmacist/staff member who calls IRT and prepares the challenge product) and participant will be blinded as to which day he/she receives which challenge.

Screening Visit 1 - after all inclusion and exclusion criteria are confirmed, but before Screening Visit 2 begins, the site's unblinded staff responsible for preparing the allergen/placebo product for the challenge will call the IRT system to randomize the participant to the order in which they will receive the peanut allergen and placebo during DBPCFC parts 1A and 1B. The participant will complete the DBPCFC parts 1A and 1B. A minimum of 30 minutes after the last dose is given for part 1B, the site can unblind the staff and participant to confirm the final exclusion criteria. Unblinding will enable the site staff to determine if the participant met the exclusion criteria for having a reaction to placebo (see [Section 5.2](#)). If no reaction to placebo, the participant may proceed to study treatment randomization, Day 1.

Randomization (Day 1) - Randomization through IRT will take place on Day 1 to randomize the participant to one of five study treatment arms. The investigator or his/her delegate will contact the IRT after confirming that the participant fulfills all the inclusion/exclusion criteria. The IRT will assign a randomization number to the participant, which will be used to link the participant to a treatment arm and will specify a unique medication number for the first package of study treatment to be dispensed to the participant.

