**Table 6-5 Blinding Schema**

Role	Randomization (Treatment)	DBPCFC sequence randomization*	Study drug allocation and Dosing	Safety event(s)	Interim analysis
Participants	B	B	B	B	B
Investigator and site staff	B	B	B	B	B
Site staff for study drug (IMP)	B	B	B	B	B
Site staff unblinded for DBPCFC product preparation	B	UI	B	B	B
Global clinical supply and randomization office	UI	UI	UI	UI	UI
Sponsor CTT	UI	B	B	UI	UI
Pharmacovigilance	UI	B	B	UI	UI
Sponsor CRA and CSM	B	B	B	B	B
Sponsor statistician	B	B	B	B	UI
Sponsor PK/PD team	UI	B	B	UI	UI

B- Blinded

UI – Unblinded

\* For the peanut/placebo product used during the DBPCF challenges: participants, site staff and sponsor staff will be blinded during the administration of the challenges. Of note, however, participants, site staff and sponsor staff will/may be unblinded after the completion of each set of DBPCFCs (after Screening Visit 2 and after Day 28). Further information on this unblinding is offered in [Section 16.4.2](#).

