### **16.4.2 DBPCFC Dosing schedule**

This study includes two DBPCFCs: the first at Screening (Visits 2 and 3), the second at the end-of-treatment (one month) (Day 26 and 28).

Each DBPCFC consists of two Parts, active allergen (peanut) challenge and placebo challenge. Each challenge is to be performed on a separate day (part 1A and 1B during screening, and part 2A and 2B at end-of-treatment period). The active allergen challenge is either given on the first day or the second day. To ensure and preserve the double-blind nature of the challenge, independent (unblinded) study site staff need to prepare the material for each challenge prior to administration. Study staff/investigator administering the challenge and Participants undergoing the challenge remain blinded to the identity of the challenge on the two test days (i.e. if peanut allergen or placebo is tested on the first or the second day). The time interval between each challenge is two to seven days; there must be a minimum of two full days and a maximum of 7 days between part 1A or 2A and part 1B or 2B DBPCFCs. There must be at least

72 hours between the completion of the DBPCFC part 1B and the first administration of study treatment at the randomization visit.

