#### **16.4.4 Allergen material**

Novartis will supply the Oral Food Allergen Peanut Flour Chocolate Meal Base and its placebo globally in an open-label fashion.

- high dose: 20%w/w Peanut Flour Chocolate Flavour Challenge Meal Base (20%w/w Peanut Choc)
- low dose: 0.67%w/w Peanut Flour Chocolate Flavour Challenge Meal Base (0.67%w/w Peanut Choc)
- Placebo: 0%w/w Peanut Flour Chocolate Flavour Challenge Meal Base (0%w/w Peanut Choc)

Pharmaceutical Dosage Form: Granules for oral suspension

Route of Administration: Oral

The food challenge material and preparation instructions are described in detail in the LOU064I12201 Pharmacy Manual provided separately.

As previously noted, there should be an independent, unblinded staff member, or other appropriately trained study site staff to prepare (i.e. NOT TO ADMINISTER) the unblinded material for the DBPCFC after obtaining the assigned test sequence through the IRT system [Section 16.4.2](#).

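### Protocol 6.5 lets staff who know the challenge material administer it, contradicting Appendix 4 and creating a cueing risk at the challenge that yields the primary endpoint

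*Protocol*

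**What the plan says.** **Who may know the challenge sequence.** Protocol 6.5 lists exceptions to the sequence blind. One is the site pharmacist or trained staff "responsible for randomizing, preparing (reconstituting), dosing and administering the peanut allergen and placebo used during the DBPCFCs". A later bullet in 6.5 requires the identity of the material to be concealed so as to maintain "blinding of the participant, investigator and other site staff not involved with the preparation and administration of the product". Both bullets treat administration as part of the unblinded role.

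Appendix 4 separates the two roles. Section 16.4.2 states: "Study staff/investigator administering the challenge and Participants undergoing the challenge remain blinded to the identity of the challenge on the two test days". Section 16.4.4 calls for an independent, unblinded person "to prepare (i.e. NOT TO ADMINISTER) the unblinded material for the DBPCFC". Section 3 says that the participant and all study staff, "except the unblinded pharmacist/staff member who will re-constitute the allergen, will be blinded to which visit administers which". Section 6.4.2 likewise exempts only the person who calls the IRT and prepares the product. At site level, Table 6-5 marks only the product-preparation staff as unblinded to sequence.

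**When, and to whom, the screening sequence is opened.** The Table 6-5 footnote says that participants, site staff and sponsor staff "will/may be unblinded after the completion of each set of DBPCFCs", and then gives the times as "after Screening Visit 2 and after Day 28". Sections 3, 6.4.2, 6.5 and 8.1 all place the screening unblinding after part 1B, at Screening Visit 3. On who is told, 6.4.2 says that "the site can unblind the staff and participant to confirm the final exclusion criteria", whereas 6.5 restricts it to site staff.

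**The concern.** Section 6.5 is the governing blinding section, so a site may reasonably staff the challenge from it. If it does, the person handing over up to nine escalating doses on Days 26 and 28 may know whether they contain peanut.

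This matters because the outcome is judged in the room:

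- Under 16.4.6 a combination of mild symptoms can be dose-limiting at the investigator's discretion.
- Several moderate, dose-limiting items in Table 16-6, such as throat tightness, abdominal pain and nausea, depend largely on what the participant reports.
- Under 16.4.3 the investigator may lengthen the interval or stop the challenge after a reaction, and a challenge still in doubt after one hour counts as positive.

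Section 16.4.1 itself relies on the double blind to limit bias in interpreting the test. Through tone, hesitation or vigilance, an administrator who knows the material could influence what the participant reports or how the investigator reads it.

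**Working it through.** No power, alpha or sample-size figure bears on this point, so the check is a comparison of the texts.

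**Step 1: may the unblinded person administer the challenge?**

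| Place in Protocol | Role unblinded to sequence | Person administering |
|---|---|---|
| 6.5, exceptions list | randomizes, prepares, doses, administers | unblinded |
| 6.5, concealment bullet | staff involved in preparation and administration | blind not protected |
| 3 | person who reconstitutes | blinded |
| 6.4.2 | person who calls the IRT and prepares | blinded |
| Table 6-5 | product-preparation staff | blinded during administration (footnote) |
| 16.4.2 | independent preparer | blinded |
| 16.4.4 | preparer, barred from administering | a different person |

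The two bullets in 6.5 stand against five other places. The conflict is direct: a site cannot use the 6.5 exception for administration and also comply with 16.4.2 and 16.4.4.

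**Step 2: which challenge does the 6.5 wording reach?** It refers to the challenges in general, so it covers screening and end of treatment. The primary endpoint comes only from the one-month challenge (2.1), so this wording does reach the primary endpoint.

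**Step 3: which blind is at risk?** Only the blind to challenge material. Table 6-5 keeps participants, investigator, site staff and the challenge preparer blinded to treatment arm. Section 6.5 keeps participants and investigator staff blinded to arm until database lock.

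**Step 4: what does the Table 6-5 footnote affect?** Screening Visit 2 is part 1A. Each set has one peanut day and one placebo day, so opening the sequence after part 1A reveals part 1B by elimination. The screening challenge determines inclusion criterion 6 and exclusion criterion 5, and it supplies the baseline tolerated-dose covariate (Protocol 12.4.2, SAP 2.5.2). Failing inclusion 6 also removes a participant from the PD analysis set (SAP Table 2-1). The Day 26/28 order is randomized afresh (6.4.2), and the footnote opens it only after Day 28. The footnote error therefore cannot reveal the end-of-treatment order.

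The footnote also contradicts itself, because a set is complete only after part 1B. It refers to 16.4.2 for details, but that section gives no time of unblinding.

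**Step 5: who is told after part 1B?** There are three answers: site staff only (6.5); staff and participant (6.4.2); participants, site staff and sponsor staff (Table 6-5 footnote).

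**Scale.** With the planned completers in Protocol 12.8.1, one changed call moves a one-month active arm by 1/14 = 7.1 percentage points and the placebo arm by 1/7 = 14.3 points. This shows how coarse the endpoint is. It does not estimate how often cueing would change a call.

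**The case against.** The strongest reply is that the intended design is clear and well protected. Section 6.5 itself still requires concealment from the participant and the investigator. The call on combined mild symptoms belongs to the investigator, who must follow the severity score (16.4.6), and mild symptoms are described as not usually dose-limiting. All of this stands. It means that an unblinded administrator is a source of cueing and not, in itself, an unblinded assessor. It does not remove the contradiction or tell a site which section to follow.

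Three stronger readings are tempting, and the documents do not support them.

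- A reader might infer that the Table 6-5 footnote also lets the primary-outcome blind be broken. It does not, because the Day 26/28 order is a new randomization. The assessment schedule provides for unblinding at parts 1B and 2B only, so the footnote reads as a slip for Screening Visit 3.
- A reader might infer bias between treatment arms. Neither passage opens the treatment assignment, so this does not follow directly.
- A reader might apply an assumed false-positive rate f to response rates of 80% and 5%, shrinking the 75-point difference to 75 × 0.90 = 67.5 at f = 10% or 75 × 0.80 = 60 at f = 20%. Nothing in the documents supports any value of f, or one f applied to every true responder. The 80% is in the Amendment 02 rationale, but the planned placebo rate is redacted. The 5% appears only as the centre of a prior in a supplementary analysis (SAP 2.5.5).

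The differing rules on telling the participant after part 1B concern a finished challenge, and no route from them to bias is shown. They need reconciling for consistency only.

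**Conclusion.** Section 6.5 is wrong as written. It contradicts 16.4.2, 16.4.4, Section 3, 6.4.2 and Table 6-5 on whether a person who knows the challenge material may administer it, and its wording covers the Day 26/28 challenge. The consequence is a risk of cueing while the primary endpoint is judged. That risk arises only at sites that staff the challenge according to 6.5 instead of Appendix 4, and the documents do not show whether any did. No size of effect can be derived. This is an internal inconsistency in the protocol, not a flaw in the chosen design, and it should be corrected because it concerns how the primary outcome is obtained.

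The footnote error is a separate minor item, confined to screening eligibility and the baseline covariate, both settled before treatment randomization.

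**What to change.** **Main change, Protocol 6.5.**

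1. In the list of exceptions, limit the role to staff who randomize and prepare (reconstitute) the challenge material, and delete the reference to dosing and administering.
2. In the concealment bullet, limit the excluded group to staff involved with preparation of the product. If only the first bullet is edited, the conflict with 16.4.2 remains.

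**Minor change, screening unblinding.**

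3. Correct the Table 6-5 footnote to Screening Visit 3 (part 1B) and Day 28 (part 2B), and replace its pointer to 16.4.2 with one to a section that gives the timing.
4. State one rule across 6.4.2, 6.5 and the footnote on who is told the sequence after part 1B.

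**Cost.** A protocol clarification and a site memo. No extra staff are needed, because 16.4.2 already requires an independent preparer. For challenges already done, the sponsor can check site records, where they show it, for who gave the doses, and do so before final database lock.

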**Table 6-5 Blinding Schema**

Role	Randomization (Treatment)	DBPCFC sequence randomization*	Study drug allocation and Dosing	Safety event(s)	Interim analysis
Participants	B	B	B	B	B
Investigator and site staff	B	B	B	B	B
Site staff for study drug (IMP)	B	B	B	B	B
Site staff unblinded for DBPCFC product preparation	B	UI	B	B	B
Global clinical supply and randomization office	UI	UI	UI	UI	UI
Sponsor CTT	UI	B	B	UI	UI
Pharmacovigilance	UI	B	B	UI	UI
Sponsor CRA and CSM	B	B	B	B	B
Sponsor statistician	B	B	B	B	UI
Sponsor PK/PD team	UI	B	B	UI	UI

B- Blinded

UI – Unblinded

\* For the peanut/placebo product used during the DBPCF challenges: participants, site staff and sponsor staff will be blinded during the administration of the challenges. Of note, however, participants, site staff and sponsor staff will/may be unblinded after the completion of each set of DBPCFCs (after Screening Visit 2 and after Day 28). Further information on this unblinding is offered in [Section 16.4.2](#).

## **6.6 Dose escalation and dose modification**

Investigational or other study treatment dose adjustments and/or interruptions are not permitted, except if required to manage an adverse event when a participant is deemed to be at a significant safety risk unless administration of investigational treatment is temporarily interrupted. Study drug dose adjustments are not permitted.

Any interruption of study drug administration should be discussed with Novartis or delegate regarding the participant's eligibility to continue investigational treatment.

Any missed or altered study drug administration must be recorded on the appropriate eCRF in order to reconstruct an accurate dosing history for each participant.

## **6.7 Additional treatment guidance**

### **6.7.1 Treatment compliance**

Participants will be required to take their prescribed regimen **CCI** for 28 (up to 34, pending scheduling of end of treatment DBPCFC visits) consecutive days between Days 1 and 28. Participants who: a.) discontinue study treatment prior to the end-of-treatment assessment visits starting on Day 26, OR b.) miss more than 20% of study doses throughout the treatment period, OR c.) miss medication doses for  $\geq 3$  consecutive days in the in the seven days prior to end-of-treatment DBPCFC, will not undergo the end-of-treatment DBPCFC.

The investigator must promote compliance by instructing the participant to take the study treatment exactly as prescribed and by stating that compliance is necessary for the validity of the study. The participant must also be instructed to contact the investigator if he/she is unable for any reason to take the study treatment as prescribed. Compliance will be assessed by the investigator and/or study personnel at each visit using tablet counts (if applicable) and information provided by the participant. This information should be captured in the source document at each visit, and missed doses should be recorded in the eCRF. All study treatment dispensed and returned must be recorded in the Drug Accountability Log.

Discontinuation of treatment prior to end-of-treatment assessments: Participants who discontinue treatment prior to Day 26 (DBPCFC part 2A) due to any reasons other than adverse event OR who miss more than 20% of study doses throughout the study treatment period OR who miss ANY medication doses for  $\geq 3$  consecutive days in the seven days prior to Day 26 (DBPCFC part 2A) will not undergo end-of-treatment DBPCFC part 2A or 2B. Those participants who discontinue treatment after an adverse event, but who resume therapy after discussion between investigator and sponsor, AND who have not missed more than 20% of study doses throughout the treatment period AND have not missed ANY medication doses for  $\geq 3$  consecutive days in the seven days prior to end-of-treatment DBPCFC part 2A (Day 26) WILL undergo end-of-treatment DBPCFC, part 2A and 2B. Participants who discontinue due to noncompliance of study treatment may be replaced after discussion with Novartis.

